2.2.2 INNOVATION

This study represents innovation at three levels: (1) Conceptual novelty: To date, three largely nonoverlapping lines of research have characterized the association between (i) insomnia and depression, (ii)depression and ERN function, (iii) sleep and ERN function. Together, these lines of research suggest that maladaptive ERN function may be an intermediate step between insomnia and depression, and that sleep is a modifiable target through which emotional distress can be reduced. However, this study represents the first study to explicitly evaluate ERN engagement as a mediator and predictor of depressive symptom improvement following an insomnia intervention. As such, these aims will clarify mechanisms through which insomnia can lead to other depressive symptoms and help develop personalized, mechanism-focused preventative strategies and treatments. The current approach represents a necessary first step in identifying individuals in which depression is a direct consequence of insomnia. (2) Methodological & Technical: Our study implements a multimodal, neuroimaging approach that fuses sleep EEG with full-scalp coverage, fMRI, and ERN function assessments during emotion reactivity and regulation. While each technique alone has proven useful in the context of depression research, combining these techniques promises to elucidate ERN engagement and sleep physiology mechanisms that mediate changes in depressive symptoms following a sleep intervention in a manner not previously possible. Moreover, by capitalizing on these multimodal domains, we can more clearly identify individuals whose depression is caused by insomnia and thus who are mostly likely to benefit from such an intervention. (3) Public & Mental health: While depression is one of the most prevalent and costly psychiatric conditions across the lifespan, there are currently no means to tailor treatment to a specific, underlying dysfunction. A major outcome of this study will therefore be a novel and clinically-useful mechanistic model that predicts treatment response to better treat depressed individuals with co-morbid insomnia.

2.3 RISK/BENEFIT ASSESSMENT

2.3.1 KNOWN POTENTIAL RISKS

From past experience, potential risk to participants is expected to be minimal. During data collection, the potential risks to participants will be as follows:

Brain Imaging Assessments: The principal piece of equipment used in this protocol is a 3 Tesla GE magnetic resonance imaging (MRI) scanner. The risks associated with MRI are minimal. A small number of people may feel claustrophobic inside the machine. The study will be immediately stopped via button press if this occurs. Study personnel and technicians will be on site during all acquisitions to address any such discomfort. To minimize fatigue, sufficient breaks are provided to participants during the scanning procedure, and the experimenter regularly inquires as to whether there is anything that s/he can do to facilitate the participant's comfort. Routine contraindications to MRI include presence of any metal implants (pacemaker, aneurysm clips, neurostimulators, cochlear, eyes, tattoos with ink contraindicated for MRI scanning). All participants will be appropriately screened for the presence of any such implants and/or health conditions that prohibit their MRI scanning for research purposes, using Stanford's CNI MRI screening forms. Participants who can participate in the MRI session will be screened with a metal detector before entering the magnet room for their safety. During

the scan there is a slight risk participants might experience changes in temperature in specific body parts or peripheral nerve stimulation despite adequate measures taken to prevent these from occurring. Study personnel and MRI technologists will be on site during all acquisitions and will be trained to monitor and address any such discomfort in a timely manner. Upon participation in MRI studies, research subjects are exposed to the risk of a brain abnormality being observed. We will follow an established procedure to inform and protect our research participants in case of an incidental MRI finding.

Ambulatory Polysomnographic Recording: The polysomnographic evaluation is strictly non-invasive. The equipment is well-maintained and appropriate grounding procedures are used to protect participants. Small sensors (electrodes) are positioned on the participant's scalp, face and body. Minor skin irritation may result from the application of these electrodes. Other than the time duration, there are no known adverse effects on participants resulting from either the assessment procedures. Some participants may have face or bodily hair that may cause minor discomfort during removal similar to a bandage. Disposable razors will be available for participants who wish to remove hair prior electrode placement.

Self-Report and Cognitive Assessments: The risks associated with the web-based self-report and cognitive assessments are minimal. They have not caused distress in the 5,000 healthy participants or the 1,100 patients who have completed these assessments in prior studies

Cognitive Behavioral Therapy for Insomnia Intervention: The CBT-I intervention has been well tolerated in the past. The study therapist will be experienced and sensitive to clinical issues. While treatments are intended to contribute to the development of nonpharmacological alternatives to current treatments for insomnia with comorbid emotional distress, the treatment protocol is not intended as a withdrawal procedure from sleeping medications. Those volunteers who are taking sleeping or other psychotropic medications at the time of recruitment will be admitted to the study only if they withdraw from the medication under the supervision of their physician. They may then be evaluated for inclusion in the study when they have been successfully withdrawn from the medication for a minimum of three weeks. Thus, no side-effects of medication withdrawal in these patients is planned as part of the treatment protocol.

COVID-19 Mitigation: There is a risk of contracting COVID-19 as a result of interacting with new individuals and places. The research team has put together mitigation protocols to help minimize the risk of contracting COVID-19. All researchers and participants will be required to wear face coverings, use hand sanitizer upon entering buildings, observe room density requirements set forth by Stanford, and maintain social distancing (> 6 feet separation) throughout the session when possible. There will be times during the scanning session and sleep recording hook-up where it will not be possible to maintain social distance. During these times researchers will wear additional protective equipment including a face shield to minimize potential exposure. Researchers will disinfect all surfaces and equipment the participant comes into contact with. Researchers will be required to complete a Health Check prior to entering the lab. Participants will complete a COVID-19 screening call prior to arrival on campus. Only researchers and participants who do not present symptoms of COVID-19 will be allowed to participate in research.

All interviews, questionnaires, and laboratory procedures have been carefully selected with regard to their reliability and validity, their relevance to the hypotheses of the study, and evidence from prior research (in our own laboratories and as reported in the literature) that these methods can be used without adverse effects on the participants.

2.3.2 KNOWN POTENTIAL BENEFITS

Participants are expected to benefit from this proposal since CBT-I has been shown to be efficacious for treating insomnia. Further, recent studies including preliminary data from our own lab, have found that these benefits

may go beyond treating insomnia, but also alleviating other emotional distress including anxiety and depressive symptoms. Additionally, results of the proposed study may help to identify which individuals would benefit from a sleep intervention as well as develop new interventions for other individuals with similar conditions and guide future research endeavors. Other potential benefits include 1) participants will have their psychiatric symptoms evaluated by a trained Clinical Psychologist; 2) participants' quality of life may be improved. Overall, the risk/benefit ratio is favorable since the procedures used in the research study are similar to those used in clinical practice.

2.3.3 ASSESSMENT OF POTENTIAL RISKS AND BENEFITS

This innovative project contributes to the understanding how sleep disruption and emotion regulation brain functions contribute depressive symptoms. The outcomes will help further a neural system-based understanding of emotional distress-related dysfunction that arises from loss of sleep, and may be remedied with a sleep intervention. Understanding these neural and sleep mechanisms will advance the evidence base for classification and treatment personalization for this population. Thus, the benefit to society could be substantial.

Although all research has risks, the risks to patients of the proposed research are well understood and will be explained to participants. There is little risk from the assessment procedures.

The long-term potential benefit of this research is to provide a neural and sleep based model to support classification and clinical management of depressive symptoms that arise from sleep disruption. Reflecting these goals, the potential benefits of the research are substantial. The risks associated with participation in these studies are minimal compared to the potential benefits of improvement for clinical practice.

3 OBJECTIVES AND ENDPOINTS

3.1 PRIMARY OBJECTIVES

3.1.1 GO/NO-GO MILESTONES

- 1. Feasibility of recruitment and retention: enroll 70 participants and retain ≥80% at 11 weeks. In our study of older adults (mean age=68.51, SD=5.78) described above, 87% of our sample was retained at the end of treatment visit at 11 weeks. In a prior study that included adults with comorbid depression and insomnia (mean age=47.4, SD=12.6), 93% of the individuals completed treatment⁸¹.
- 2. Emotion Regulation Network Target Engagement: This will be determined using the precision interval approach. The goal is to demonstrate sufficient variation for further investigation 82,83 . We hypothesize that CBT-I will improve ERN function by reducing amygdala reactivity and increasing amygdala-mPFC connectivity. Thus, for the amygdala, improvement is likely reflected in an absolute negative mean change value with a lower fixed-width interval boundary (M-SD/2), where M is the mean and SD is the standard deviation, which is also substantially in the negative direction. Similarly, the amygdala-mPFC improvement is reflected by an absolute increase mean change with an upper fixed-width interval boundary (M+SD/2). For a GO decision, we will require at least 1 of 3 emotion regulation neuroimaging tasks must exhibit improvement by having both a group mean change of amygdala activation with symmetric 1 SD intervals whose lower bound is less than an absolute precision criterion of (M-SD/2) \leq -0.35, and a positive group mean change of the amygdala-mPFC connectivity whose upper bound is greater than an absolute precision criteria of (M+SD/2) \geq 0.35. The criterion \pm 0.35 was selected as a value

clearly indicating more than "noise," as it places a substantial portion of the subjects in the improvement range, and thus is of potential clinical importance to warrant further study⁸².

3.1.2 PRIMARY ANALYSES

We hypothesize that in this single-arm study treatment with CBT-I will lead to improvements in Emotion Regulation Network function. Specifically, we predict that sleep restoration will be associated with greater decreases in amygdala reactivity and increases in mPFC-Amygdala Connectivity. An extended analysis of covariance (ANCOVA) will be used to test the primary hypothesis of change in Emotion Regulation Network function from baseline to end of treatment. We will characterize the association between our primary measures of Emotion Regulation Network function and that of our proximal outcome (sleep disruption as defined by sleep-EEG derived sleep efficiency) using a regression framework with age and sex included as covariates.

3.1.3 SECONDARY ANALYSES

We will examine the treatment effect on outcomes as measured by validated self-report questionnaires and sleep disruption measurements. We will also examine the association of change in Emotion Regulation Network function with change in outcomes from other domains. We will also explore associations between emotion regulation related behaviors and physiology including behavior on the neuroimaging emotion regulation tasks (implicit threat priming, emotional conflict, and emotional response), measures of emotional reappraisal and suppression as assessed with the Emotion Regulation Questionnaire and the other domains, and Respiratory Sinus Arrhythmia (RSA). The statistical approach to analysis of the treatment effect on these outcomes will use ANCOVA, analogous to the analysis of target engagement (above).

Some measures will be collected daily (e.g. actigraphy and sleep logs) and weekly (BAI, BDI, CSSRS, BSS) over the course of treatment. Our general approach is to apply mixed linear models, using the daily/weekly reports to construct an individual specific estimate (functionally the mean and coefficient of variation of daily measurements for each naturalistic measure over a week) for baseline and follow-up, and then testing the effect of time (thus testing the within-person change over time). Random intercepts and slopes (and their covariance) at the person level will be included in our models. Random intercepts will be used to account for the clustering of observations within individuals across time; random slopes for key within-person predictors (e.g. 'time' or pre to post in this case) will be included to allow within-person slopes to be stronger for some individuals and weaker for others. In cases where random slopes are observed, we will test for potential subgroups/moderation (e.g., by age, sex, etc.; although we note that the small sample size somewhat limits our statistical power for such moderation tests).

3.2 EXPLORATORY ANALYSES

3.3 STUDY MEASURES

All study measures will be collected at baseline and at the week 11 end of treatment visit. The primary study measures are listed in **Table 1** and the secondary measures are listed in **Table 2**.

Table 1a. Primary Endpoints

Purpose	Construct	Paradigm/Method	Domain	Measure (or region) of interest
	Emotion	Supraliminal emotional reactivity paradigm (Faces)	fMRI	Amygdala reactivity and mPFC-Amygdala Connectivity
Mechanistic Target, Response, & Predictive Biomarker	Regulation Network function	Subliminal emotional reactivity paradigm (Faces)	fMRI	Amygdala reactivity and mPFC-Amygdala Connectivity
Бютагкег		Emotion Regulation Task (images)	fMRI	Amygdala reactivity and mPFC-Amygdala connectivity
Clinical outcome (R61)	Insomnia	Sleep Architecture	PSG	Sleep Efficiency (SE)
Clinical outcome (R33)	Depression	Beck Depression Inventory	Self Report	Total score after excluding the sleep items

Abbreviations: functional Magnetic Resonance Imaging (fMRI); medial Prefrontal Cortex (mPFC); Polysomnography (PSG);

Table 2. Secondary Endpoints

Construct	Paradigm/Method	Domain	Measure (or region) of interest
	RSA	Physiology	Respiratory Sinus Arrhythmia during a paced breathing task
Faration	Emotion Task HRV	Physiology	HRV recorded simultaneously with fMRI during tasks
Emotion regulation	Threat Priming	Behavior	Reaction time and memory for threat/happy primed faces
regulation	Emotional Response	Behavior	Ratings of emotional stimuli during emotion regulation task
	Emotion Regulation	Self Report	Emotion regulation ability assessed by the ERQ, DERS, TAS-20
	Sleep Continuity	Actigraphy	WASO, TST, SE, SOL, # of arousals, as measured by actigraphy
	Sleep Architecture	PSG	WASO, TST, TIB, SOL, # of arousals, duration in REM/NREM, etc.
Sleep Disturbance	Sleep Physiology	PSG	Power density spectral analysis of Delta, Theta, Alpha, Sigma, beta & Gamma bands across electrodes and sleep stages.
	Sleep HRV	Physiology	HRV recorded during sleep initiation and sleep stages
	Sleep Complaints	Self Report	Subjective complaints of insomnia as measured by the ISI
	Suicidality	Self Report	Suicidal ideation and behaviors as assessed by the S-STS
	Anxiety	Self Report	Anxiety symptoms assessed by the BAI and GAD-7
	Depression	Self Report	Depressive symptoms assessed by the PHQ-9
Emotional Distress	Rumination	Self Report	Assessed by the RRS-short and PSWQ
Distress	Anhedonia	Self Report	Assessed by the SHAPS
	Mood States	Self Report	Assessed by the Profile of Mood States (POMS)
	Irritability	Self Report	Assessed by the CHICa
Current	Quality of Life	Self Report	Assessed by the WHOQOL and SF-36
Functioning	Cognitive function	Behavior	Assessed by the RBANS and Emotional Face Recognition task

Abbreviations: Heart Rate Variablity (HRV); Emotion Regulation Questionnaire (ERQ)⁸⁴; Wake After Sleep Onset (WASO); Total Sleep Time (TST); Sleep Efficiency (SE); Sleep Onset Latency (SOL); Rapid-Eye Movement Sleep (REM); Non-REM (NREM); World Health Organization Quality of Life

(WHOQo); Repeatable Battery for the Assessment of Neuropsychological Status(RBANS)85

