Additionally, we hypothesize that improvements in fronto-limbic brain function will be associated with parallel improvements in both primary and secondary measures of depression and sleep outcomes. We will test these hypotheses using linear regression with fronto-limbic activation and connectivity change scores (post-treatment minus pre-treatment) as predictors and depression or sleep change scores as outcomes. Diagnostic checks revealed that residuals were not normally distributed for models including changes in suicidal thinking as the outcome (Shapiro-Wilk test, p < 0.05). Therefore, we will use a non-parametric bootstrap with 5,000 resamples (R package 'boot') to derive confidence intervals and p-values for each predictor. We report the original OLS coefficients (b), along with 95% bias-corrected and accelerated (BCa) confidence intervals and two-sided p-values derived from the bootstrap distributions.

We will also examine whether changes in objective and subjective insomnia symptoms are related to depression symptom improvements using OLS regression. We expect the degree of depression symptom improvement will be associated with increased sleep efficiency and reduced self-reported insomnia symptoms. Models including BSSI as the depression change outcome will use non-parametric bootstrap to derive confidence intervals and p-values.

Last, we aim to test whether pre-treatment inter-individual differences in fronto-limbic brain activity and connectivity, objective sleep efficiency, and self-reported insomnia symptoms are predictive of the magnitude of depression symptom improvement. We specified residualized change models, which isolate the relationships between pre-treatment inter-individual differences and post-treatment depression symptoms, accounting for baseline depression levels. As above, models including the BSSI employed non-parametric bootstrapping to derive confidence intervals and p-values. We hypothesized that those with greater pre-treatment fronto-limbic dysfunction (higher amygdala reactivity and lower amygdala-mPFC connectivity) and worse insomnia symptoms (lower objective sleep efficiency and higher subjective insomnia symptoms) would experience the greatest improvements in depression symptoms following CBT-I.

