Mechanistic, preclinical studies show that sleep deprivation increases anxiety and depression^{11,26-31}.

Individual differences in sleep architecture and physiology are also

[figure not shown]

associated with depressive symptoms and suicidal ideation^{19,31-36}. MDD is frequently accompanied by decreased sleep continuity and depth³⁷, which can be improved by a behavioral insomnia treatment^{38,39}. Depression is also associated with increased REM pressure³⁷. More recent work has described sleep abnormalities associated with depressive symptoms using spectral analysis of the EEG signal, including decreased delta activity during Non-Rapid Eye Movement Sleep (NREM) associated with perceptions of stress, and increased alpha activity during NREM associated with depression symptoms⁴⁰. Additionally, individual differences in REM sleep spectral profiles are associated with next-day emotion regulation network function and behavioral performance on emotion tasks^{31,32,34}. Importantly, these spectral markers are highly localized over the frontal cortex such that using full-scalp EEG, as proposed in the current application, is necessary to obtain spatial coverage and resolution necessary to detect region-specific

changes.

While limited number, these studies support the hypothesis that sleep disruption and abnormal sleep physiology may be a causal risk factor in development, the maintenance, and exacerbation depressive other indicators of emotional distress in psychiatric

disorders. Critically,

of Figure 2. Preliminary Data: Associations between insomnia (ISI) and depressive symptoms (BDI after excluding the sleep items). Data from 106 older adults seeking treatment for insomnia. This symptoms as well as study excluded Axis-I diagnoses. A. Insomnia was associated with depressive symptoms at baseline. B. Depressive symptoms decreased after receiving CBT-I C. The reduction in insomnia severity was associated with the reduction in depressive symptoms, such that those with the greatest reduction in insomnia experienced the greatest reduction in other depressive symptoms.

there is evidence from PI [name]'s (Figure 2) that sleep disruption is a modifiable target that can reduce other depressive symptoms, including suicide risk specifically, making sleep-targeted behavioral therapies attractive and tractable therapeutic opportunities. Findings from

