These same regions are impaired experimentally induced and naturalistic sleep disruption (including insomnia) and may be improved by intervening sleep. Acute sleep deprivation, sleep restriction, and poor habitual sleep (including insomnia) all amplify amygdala reactivity to negative experiences 30,31,73-77. This signature of excessive amygdala reactivity caused by sleep disruption, has routinely been linked to decreases in functional connectivity with the mPFC⁷³⁻⁷⁷. These alterations in brain function are also paired with changes in affective behavioral outcomes and subjective reports of significant clinical relevance. For example, inter-individual differences in mPFC-amygdala connectivity

[figure not shown]

Figure 3. Preliminary Data: Emotion regulation network function (amygdala reactivity to subliminal threat) is associated with both **A.** Depressive symptoms (BDI) and **B.** Sleep disturbance (Insomnia item of the BDI) in a sample of 87 unmedicated individuals ranging from no depression through clinical depression.

following sleep deprivation are significantly correlated with concurrent sleep-loss increases in subjective anxiety⁷⁶. Preliminary data from a sample of unmedicated participants with a range of depressive symptoms, demonstrates robust associations between amygdala hyperactivity and insomnia severity as measured by the insomnia item from the BDI; this converges with evidence that insomnia symptom severity mediates known associations between depression and amygdala hyperactivity (**Figure 3**). Critically, and guiding our hypothesis that CBT-I may reduce depressive symptoms through improving ERN dysfunction, a full night of sleep normalizes

amygdala reactivity and re-establishes mPFC-amygdala connectivity the following day^{32} . Taken together with aforementioned background this evidence strongly suggests that sleep disruption, including insomnia, causes dysfunctional brain state as well as emotional distress that strongly resembles that of MDD, and that may be reversible with targeted а sleep intervention.

In this R61/R33 project, we aim to test the hypothesis that alleviating insomnia reduces other depressive symptoms by normalizing ERN function (**Figure 4**). In the R61 phase, we will conduct a mechanistic

[figure not shown]

Figure 4. Conceptual frame work and Specific Aims 1 and 2 for the R33 phase

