3.3.3 DEPRESSIVE SYMTPOMS

The BDI⁸⁹ total score after removing the sleep items will be used as the primary outcome measure of depressive symptoms. Given that suicide is a risk associated with insomnia independent of other depressive symptoms, suicidality (CSSRS and BSS) will be included as a secondary outcome measure. Given the high comorbidity between insomnia, depression, and anxiety, we will also assess anxiety using the Beck Anxiety Inventory (BAI⁹⁰) as a secondary outcome. In addition to the baseline and end of treatment assessments, the BDI, BAI, BSS and CSSRS will be assessed weekly prior to each treatment session. Additional secondary measures related to specific aspects of emotional distress relevant to depression are listed in **Table 2**.

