Beck Depression Inventory (BDI)⁸⁹ . The BDI-II is a 21-item self-report scale that assesses the severity of depression symptoms. The depression items consist of: sadness, pessimism, past failure, loss of pleasure, guilty feelings, punishment feelings, self-dislike, self-criticalness, suicidal thoughts or wishes, crying, agitation, loss of interest, indecisiveness, worthlessness, loss of energy, changes in sleeping pattern, irritability, changes in appetite, concentration difficulty, tiredness or fatigue, and loss of interest in sex. Items are scored from 0 to 3, and higher scores indicate greater levels of severity. The ranges for depression are: 0-13 minimal, 14-19 mild, 20-28 moderate, and 29-63 severe. The BDI-II has high validity and reliability.

Beck Anxiety Inventory (BAI)⁹⁰. The BAI is a 21-item self-report scale that assesses the severity of anxiety symptoms. Items are scored from 0 to 3 (0 = not at all, 3 = severe). Higher scores indicate greater levels of severity, and the ranges for anxiety levels are: 0-9 normal to minimal, 10-18 mild to moderate, 19-29 moderate to severe, and 30-63 severe. The BAI consists of two factors: somatic and cognitive.

World Health Organization Quality of Life Assessment (WHOQOL)¹²². The WHOQOL-BRIEF is a 26-item brief version of the WHOQOL, that measures quality of life based on six domains: physical health, psychological state, level of independence, social relations, environment, and spirituality/religion/personal beliefs. Four general items about subjective overall QOL and health are also included. Only domain and general item scores are calculated in the WHOQOL-BREF. Items are scored on scales of 1 to 5, and higher scores indicate higher quality of life.

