Patient Health Questionnaire (PHQ-9)¹²³. PHQ-9 is a self-administered instrument for screening, diagnosing, monitoring, and measuring the severity of depression. It rates the frequency of symptoms as "0" (not at all) to "3" (nearly every day) and has been validated for use in primary care. The PHQ-9 total score ranges from 0 to 27 and is categorized as follows: None or minimal depression 0-4, Mild depression 5-9, Moderate depression 10-14, Moderately severe depression 15-19, and Severe depression 20-27. Cronbach's alpha coefficients range from 0.86 to 0.89 and test-retest correlations range from 0.84-0.95 within 48 hours and from 0.81-0.96 at 7-day reassessment. PHQ-9 scores were found to be highly correlated with Beck Depression Inventory scores in the general population (r=0.73).

Generalized Anxiety Disorder Scale (GAD-7)¹²⁴. GAD-7 is a valid and reliable 7-question scale to screen for 4 anxiety disorders: Post Traumatic Stress Disorder, Panic Disorder, Generalized Anxiety Disorder, and Social Phobia. A score of ≥ 10 indicates a high probability of 1 or more of these disorders. Cronbach's alpha is 0.92 and test-retest correlation is 0.83. GAD-7 scores also correlate highly with scores of 2 commonly- used anxiety scales: the Beck Anxiety Inventory (r=0.72) and the anxiety subscale of the Symptom Checklist-90 (r=0.74).

Emotion Regulation Questionnaire (ERQ)¹²⁵. ERQ is a 10-item self-report survey assessing individual differences in the habitual use of two emotional regulation strategies: cognitive reappraisal (6 items)

and expressive suppression (4 items). Cognitive reappraisal is a strategy that involves interpreting an emotion-eliciting situation in a way that changes its emotional impact, whereas expressive suppression is a form of response modulation that involves restraining emotion expressive behavior. The ERQ shows high levels of internal consistency in measuring both strategies in a large, diverse sample (Reappraisal factor α =.79 and Suppression α =.73). Test-retest reliability across 3 months was .69 for both scales.

Penn State Worry Questionnaire (PSWQ)¹²⁶. The PSWQ is a 16-item questionnaire that aims to measure the trait of worry, using Likert rating from 1 (not at all typical of me) to 5 (very typical of me). Research suggests that the instrument has a strong ability to differentiate patients with generalized anxiety disorder (GAD) for other anxiety disorders.

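### The plan removes the sleep items from the BDI but states no matching rule for the PHQ-9, its secondary depression endpoint

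*Combined protocol and SAP*

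**What the plan says.** Protocol section 2.2.1 gives the aim: to "test the hypothesis that alleviating insomnia reduces other depressive symptoms by normalizing ERN function". Scoring of the BDI follows from it. Table 1a in section 3.3 lists the BDI as "Total score after excluding the sleep items", and section 3.3.3 says that the BDI "total score after removing the sleep items will be used as the primary outcome measure of depressive symptoms". The preliminary data in section 2.2.1 (Figure 2) follow the same rule: "Associations between insomnia (ISI) and depressive symptoms (BDI after excluding the sleep items".

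For the PHQ-9, Table 2 says only "Depressive symptoms assessed by the PHQ-9". Section 8.1.3 describes symptoms rated 0 to 3 and adds: "The PHQ-9 total score ranges from 0 to 27". Section 9.4.3 lists it among the secondary emotional-distress outcomes to be tested for a treatment effect. No section of either document removes a PHQ-9 item or plans a sensitivity score.

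The SAP does not name the PHQ-9. It relates change in brain function to "parallel improvements in both primary and secondary measures of depression and sleep outcomes", and then regresses depression improvement on change in objective sleep efficiency and in self-reported insomnia. Protocol section 9.2 adds a screen: measures whose improvement goes with improvement in sleep at R2 = 0.10 are kept for the R33 phase.

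**The concern.** The investigators treat sleep content in a depression scale as a problem and solve it for one of their two depression scales. If the PHQ-9 keeps a sleep item, part of its change is the sleep benefit that CBT-I is expected to produce, and three analyses are exposed:

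- **Pre-post test of the PHQ-9.** A fall in the sleep item counts as improvement in depression.
- **Regression of depression change on ISI change.** Outcome and predictor share sleep content, so some association is built in. This applies if the SAP's secondary depression measures include the PHQ-9.
- **Section 9.2 screen.** A depression score that contains a sleep item has an advantage when measures are retained for their link with sleep improvement.

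The sleep-free BDI and the PHQ-9 could then disagree merely because one of them counts sleep, and the plan has no rule for reading such a disagreement.

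**Working it through.** **Inputs from the documents.** PHQ-9 items are scored 0-3 with a maximum of 27 (section 8.1.3). N = 56, which is 80% of 70 (section 9.2). The screen is R2 = 0.10 (section 9.2).

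**Assumptions, not in the documents.** One PHQ-9 item asks about sleep. The SD of its change, s1, is 0.8 to 1.0 (central 0.9). The SD of change in the sum of the other eight items, s8, is 3 to 5 (central 4). The correlation of sleep-item change with ISI change, r, is 0.4 to 0.8 (central 0.6). The other eight items have no mean change and no relation to the sleep item or the ISI.

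**1. Score range.** 27 / 3 = 9 items, so the stated range counts every item. Without one item it is 8 x 3 = 24. The sleep item carries at most 3 / 27 = 11.1% of the scale. Example: the sleep item falls from 3 to 1 and no non-sleep symptom changes. The PHQ-9 total changes by -2, and the BDI as scored in this plan changes by 0.

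**2. Built-in correlation with ISI change.** rho = r x s1 / sqrt(s1^2 + s8^2).

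- Central: 0.6 x 0.9 / sqrt(0.81 + 16) = 0.54 / 4.10 = 0.13, so R2 is about 0.017.
- Lowest: 0.4 x 0.8 / sqrt(0.64 + 25) = 0.32 / 5.06 = 0.06, R2 = 0.004.
- Highest: 0.8 x 1.0 / sqrt(1 + 9) = 0.80 / 3.16 = 0.25, R2 = 0.064.

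Overlap alone therefore leaves the true R2 below the 0.10 threshold throughout.

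**3. Chance results at N = 56 (simulated).** A correlation reaches two-sided p < 0.05 at |r| = 0.263 and passes the screen at r = sqrt(0.10) = 0.316.

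| | No overlap | Central | Range |
|---|---|---|---|
| p < 0.05 against ISI change | 5% | 16% | 8-47% |
| R2 at least 0.10, expected direction | 0.8% | 8% | 3-31% |

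Fisher's z agrees at the centre. For p < 0.05, (0.2696 - 0.1325) x sqrt(53) = 1.00, an upper tail of 16%. For the screen, (0.3275 - 0.1325) x sqrt(53) = 1.42, a tail of 8%.

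**4. Pre-post test.** A paired t-test stands in for the planned model. If only the sleep item changes, d = mean fall / sqrt(s1^2 + s8^2). With a mean fall of 1.0 point at central values, d = 1 / 4.10 = 0.24, and the PHQ-9 total falls significantly in about 43% of trials. With mean falls of 0.5 to 1.5 points and s8 of 3 to 5, the figure runs from 11% to 94%. Without the sleep item it is the nominal 5% (two-sided).

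**5. After removal.** Under the same assumptions the built-in correlation is 0, and the rates return to those in the no-overlap column.

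**The case against.** Much of the case against this point limits it, and that part stands.

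- **The PHQ-9 items are not printed.** Section 8.1.3 does print the BDI-II content, including "changes in sleeping pattern, irritability, changes in appetite, concentration difficulty, tiredness or fatigue". A sleep item in the PHQ-9 is an assumption here.
- **No sentence says that the full total will be analysed.** A reader might infer this from the 0-27 range, but section 8.1.3 also describes the BDI over its whole range, up to 63, and the BDI is analysed without its sleep items. The full-total reading rests on the absence of any exclusion for the PHQ-9.
- **The SAP may not mean the PHQ-9.** It treats a suicidal-ideation scale as a depression change outcome, and protocol section 3.3.3 names suicidality as a secondary outcome, so its secondary depression measures could be those.
- **The overlap is not general.** One might conclude that every PHQ-9 test relates sleep to itself. That is strictly so only for models against self-reported insomnia. The fMRI predictors share no item content with the questionnaire, and the pre-post test relates nothing to sleep, although a sleep item still contaminates it. Objective sleep efficiency should overlap less than the ISI, and section 9.2 does not say which sleep measure its screen uses.
- **The null scenario is unlikely.** Section 2.2.1 reports d = 1.45 for CBT-I on other depressive symptoms at BDI of 14 or more, and preliminary data in which change in the sleep-free BDI tracked change in insomnia.

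One might also defend a validated total as a convergent secondary measure. That is a fair reason to keep reporting it. It does not explain why the rule applied to the BDI is absent for the PHQ-9, and no document gives a reason.

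**Conclusion.** The inconsistency is real and nothing in either document resolves it: the hypothesis concerns non-sleep depressive symptoms, the BDI is scored to match, and the PHQ-9 has no stated rule. If the PHQ-9 has one sleep item and is analysed as a full total, up to 3 of 27 points can move with sleep alone, and a correlation of about 0.13 with ISI change is built in (roughly 0.06 to 0.25 over the assumed range).

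The effect is modest and confined to a secondary endpoint. It bears on the PHQ-9 pre-post test, on the section 9.2 screen, and on the insomnia-change regression if the SAP's wording covers the PHQ-9. The fMRI primary endpoint and the sleep-free BDI are not affected.

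The 43% and 16% figures should not be read as this trial's expected false-positive rates. They are worst-case illustrations that assume no change in non-sleep symptoms, which the protocol's own preliminary results make unlikely. The point still merits correction, because the remedy is cheap and the plan already accepts the principle.

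**What to change.** In Table 2, section 3.3.3 and the SAP, prespecify the PHQ-9 without its sleep item (range 0-24) for:

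1. the pre-post test;
2. every model relating depression to sleep or insomnia measures, including the SAP's baseline-predictor models;
3. the section 9.2 screen of measures against sleep improvement.

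Report the full 0-27 total alongside as a sensitivity analysis. The SAP should also say whether the PHQ-9 is one of its secondary depression measures. If a sleep-free score was always intended, one sentence saying so is enough.

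The cost is one scoring line, computed from item responses already collected. The small downside is that an eight-item score cannot be set against the severity bands in section 8.1.3. The full total still covers that use.
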